### 8.6.1.4 Procedure for Reporting an Adverse Event of Special Interest

For any AESI occurring during the clinical trial, regardless of whether or not related to the treatment, the investigator must:

- Take prompt and appropriate medical action, if necessary. The safety of subjects is the first priority.
- Ensure that the event is evaluated and recorded as an AESI in the CRF within 24 hours of receipt of the event. The CCI Safety and Pharmacovigilance group will receive automated notification of an AESI by email.

CONFIDENTIAL Page 65 of 99

Note: Immediate AESI reporting is required by the investigator if it occurs during the clinical study or within 12 weeks (± 5 days) of receiving the last dose of study drug, whether or not the event is considered to be related to the investigational product.

The demographics, medical history, drugs/therapies, and medical and surgical procedures forms must also be available for review in CRF, at that time.

- Send any relevant information or medical records (eg, laboratory test results) to the
   Safety and Pharmacovigilance group within 24 hours of receipt of this relevant information.
- Monitor and record the progress of the event until it resolves or reaches a stable condition, with or without sequelae. For all additional follow-up evaluations, update the AESI form within 24 hours of receipt of the updated information.
- Obtain and maintain in the files all pertinent medical records, information, and medical
  judgments from colleagues who participate in the treatment and follow-up of the subject. If
  necessary, contact the subject's personal physician or hospital staff to obtain further details.
- When the outcome of the event is known, update the AESI form, if appropriate.

## 8.6.1.5 Procedure for Reporting Pregnancies

Any pregnancy occurring during clinical trials, where the fetus could have been exposed to the study drug, must be monitored until its outcome in order to ensure the complete collection of safety data. If a subject becomes pregnant, the investigator must:

- Withdraw the subject from the clinical trial. The subject must not receive any further injection of the study drug.
- Complete as fully as possible the Pregnancy Surveillance Form Part I: History and Start
  of Pregnancy. Send by email or fax along with the exit form within 24 hours of receipt of
  the information, to the CCI Safety and Pharmacovigilance group. Refer to
  Section 8.6.1.3.

Note: Immediate pregnancy reporting is required by the investigator if it occurs during the clinical study or within 12 weeks ( $\pm$  5 days) of receiving the last dose of study drug, whether or not the event is considered to be related to the investigational product.

- Monitor and record the progress of the pregnancy until its outcome. Contact the subject's regular physician (general practitioner or gynecologist) or hospital staff to obtain further details and ask for regular follow-up information.
- 4. Provide tri-monthly updates until the final outcome of the pregnancy, by completing the Pregnancy Surveillance Form Part II: Course and Outcome of Pregnancy. For all additional follow-up evaluations, send the form by email or fax to the College Safety and Pharmacovigilance group within 24 hours of receipt of the information. If the subject can no longer be reached (ie, lost to follow-up), documentation of the non-response/contact with 2 phone calls and a letter (certified with return receipt) is required.

CONFIDENTIAL Page 66 of 99

At the outcome of the pregnancy, complete as fully as possible the Pregnancy Surveillance
Form – Part II: Course and Outcome of Pregnancy. Print and send the form by email or fax
to the College Safety and Pharmacovigilance group within 24 hours of receipt of the
information.

 If the pregnancy leads to an abortion (ie, voluntary abortion, spontaneous abortion or therapeutic abortion), in utero death or congenital anomaly, follow the procedure for declaration of an SAE (see Section 8.6.1.3).

### 8.6.1.6 Unexpected Adverse Reactions

## Unexpected Adverse Reaction Definition

An unexpected adverse reaction is any untoward and unintended response that is related to the administration of the study drug at any dose, the nature or severity of which is not consistent with the applicable product information (eg, reference safety information in the investigators brochure for nemolizumab, study protocol, etc).

The sponsor or its delegate (ie, CCI ) will comply with country-specific regulatory requirements relating to safety reporting to regulatory authorities, IRB / IEC and investigators. Investigator safety reports are prepared for SUSARs according to local regulatory requirements and sponsor policy, and are forwarded to investigators as necessary.

An investigator who receives an investigator safety report describing an SAE(s) or other specific safety information (eg, summary or listing of SAEs) from the sponsor or its delegate (ie, CC) will file it with the IB and will notify the IRB/IEC, if appropriate according to local requirements.

#### 8.6.2 Clinical Laboratory Evaluations

The hematology, clinical chemistry laboratory analyses, and urinalyses will be performed at a central laboratory. Reference ranges will be supplied and used by the investigator to assess the laboratory data for clinical significance and pathological changes.

The investigator or medically qualified co-investigator must review and evaluate laboratory values for each subject in a timely manner. For each out-of-range laboratory result, the investigator or designee will evaluate whether he/she considers it to be clinically significant, defined as meeting at least one of the following conditions:

- The abnormality suggests a disease and/or organ toxicity, or
- The abnormality is of a degree that requires additional active management, eg, discontinuation of the drug, close observation, more frequent follow-up assessments, or further diagnostic investigation.

If the investigator observes a clinically significant laboratory result, the test will be repeated as soon as possible and the subject will be monitored until the value returns to normal and/or an adequate explanation for the abnormality is found.

All clinically significant out-of-range laboratory values at the screening visit will be recorded (report a diagnosis rather than the laboratory value whenever possible). All clinically significant

CONFIDENTIAL Page 67 of 99

out-of-range laboratory values after the screening visit are to be reported as an AE if this abnormality was not present at the screening visit or is assessed as having worsened since the screening visit (ie, changed significantly from the screening visit). Whenever possible, the investigator should provide a diagnosis of an AE when reporting the abnormal laboratory value.

Subjects should be reminded to be well-hydrated before all visits for phlebotomy purposes. Subjects will be required to fast for at least 8 hours before the visits when blood chemistry testing is planned, except for the screening visit. The screening visit laboratory values must be available before the baseline visit.

Total blood volumes to be drawn at each visit are provided in the clinical laboratory manual. Additional samples may be required if medically indicated (eg, at unscheduled visits for safety reasons, when an abnormal laboratory value is observed and requires a re-test).

The following laboratory safety tests will be performed as specified in Section 7.2:

## 8.6.2.1 Hematology

Hemoglobin, hematocrit, white blood cell (WBC) count (with differential including eosinophils), red blood cell (RBC) count, platelet count, and mean cell volume (MCV).

#### 8.6.2.2 Clinical Chemistry

Creatinine, aspartate aminotransferase (AST), alanine aminotransferase (ALT), gamma glutamyltransferase (GGT), alkaline phosphatase, lactate dehydrogenase (LDH), total bilirubin, direct bilirubin, creatinine phosphokinase ([CPK], CPK isoenzyme test will be performed only if CPK is elevated to > 2.5 × ULN. The investigator should also contact the medical monitor in such situations.), albumin, total protein, uric acid, sodium, potassium, calcium, chloride, glucose, urea, total cholesterol, triglycerides, low-density lipoprotein (LDL), and high-density lipoprotein (HDL).

#### 8.6.2.3 Urinalysis

pH, glucose, ketones, blood, protein, leukocytes, nitrites, bilirubin, urobilinogen, and specific gravity.

## 8.6.3 Pregnancy Testing

All women of childbearing potential will have a serum pregnancy test at the screening visit and urine pregnancy tests (UPTs) at subsequent visits according to Section 7.2.

UPTs with a sensitivity < 25 IU/L, will be provided to the study centers for use in the trial.

UPTs will be performed at the study centers, and all other samples will be sent to central laboratory for analysis.

If the result of a UPT is positive, it must be confirmed with a serum pregnancy test, and no study drug should be administered pending the serum pregnancy test result.

CONFIDENTIAL Page 68 of 99

### 8.6.4 Virology

Virology including HBsAg, HBcAb, hepatitis C, HIV-1 and -2 antibody will be assessed at the screening visit.

### 8.6.5 Tuberculosis Testing

Immunosuppressant biologic treatments have been shown to increase the risk of TB infection or to cause conversion from latent to active TB in some circumstances. Because of this, subjects will be screened for active or latent TB before entry into this study.

#### 8.6.5.1 Definitions

Active TB is a disease caused by *Mycobacterium tuberculosis* in any part of the body and that is in an active state as determined by either a smear or culture taken from any source in the person's body which tests positive for TB or by radiographic evidence. Individuals with active TB are symptomatic, depending upon the location of the disease (most commonly in the lungs but also possibly in the brain, kidneys, spine, or elsewhere), and can spread the infection to others.

Latent TB is said to exist when an individual is infected with *M tuberculosis*, as evidenced by a positive Interferon Gamma Release Assay (or IGRA), such as QuantiFERON-TB Gold, but is asymptomatic and has no evidence of active infection on screening pathology or radiographic tests. Such individuals do not pass the disease to others and should commence a course of prophylactic antimycobacterial treatment to eliminate the infection and commit to completing the course of treatment.

## 8.6.5.2 Tuberculosis Screening

Ideally, as part of the medical history, the subject should be asked if they have presented with active or latent TB in the past and whether they have received a Bacillus Calmette-Guérin (or BCG) vaccination. They should also be asked if they have been in contact with any individuals known to have active TB, or been placed in any circumstances that may have exposed them to an increased risk of TB infection, such as travel to TB-endemic regions, close contact with persons with active TB, or workplace risk (eg, prison, hospitals).

A subject who tests positive for latent TB (with a positive QuantiFERON test), should be referred to the subject's treating physician for appropriate follow-up. If the result is indeterminate, the test may be repeated once. If confirmed indeterminate, the subject should then be managed as though they have a positive test result.

#### 8.6.6 Vital Signs

Vital signs will be evaluated at the screening visit and at each subsequent visit according to Section 7.2. Vital signs will include pulse rate, systolic and diastolic blood pressure (after the subject has been sitting for at least 5 minutes), and body temperature. All abnormal values at the

CONFIDENTIAL Page 69 of 99

screening visit identified as clinically significant by the investigator will be recorded. Any clinically significant changes from the screening visit will be recorded as an AE.

#### 8.6.7 Height and Weight

Height will be measured at screening and designated visits; weight will be measured at all visits. Subject must be at least 30 kg at both screening and baseline visits in order to be enrolled into this clinical trial.

Any clinically significant weight changes from the screening visit will be recorded as an AE.

#### 8.6.8 Physical Examination

Complete physical examination (PE) should be performed at all scheduled visits and any unscheduled visits for safety reasons, according to Section 7.2. A complete PE will include assessments of the head, ears, eyes, nose, throat, neck (including thyroid), skin/integumentary system, cardiovascular system, respiratory system (with respiratory assessment; see Section 8.6.9), gastrointestinal system, musculoskeletal system, lymph nodes, and nervous system.

Investigator should assess all abnormal findings for clinical significance. All clinically significant abnormal findings at the screening visit will be recorded in the Medical History form. Any clinically significant changes from the screening visit will be recorded as an AE.

## 8.6.9 Respiratory Assessments

At screening, the investigator should specifically question all subjects about any medical history of asthma and their respiratory health (eg, wheezing, allergies, infections). Subjects with a history of asthma will be questioned about the seasonality of their asthma and known triggers, such as allergens. Newly-diagnosed asthma or worsening of asthma during the study will be reported as an AESI.

#### 8.6.9.1 Asthma Control Test

Subjects with a medical history of asthma will take the Asthma Control Test (ACT) at each study visit before questioning and physical examination by the investigator. Subjects with a new (de novo) diagnosis of asthma will take the ACT beginning at the visit the diagnosis was first confirmed and thereafter, at all subsequent study visits. Subjects with an ACT score  $\leq$  19 should be referred to the physician managing their asthma.

## 8.6.9.2 Respiratory Examination

The ACT will aid the investigator's questioning of subjects with a medical history of asthma and should be completed before the clinical questioning. All subjects will be asked non-leading questions about any respiratory changes. The investigator or designee will then perform a respiratory examination of all subjects at all visits. Subjects with a medical history of asthma

CONFIDENTIAL Page 70 of 99

should be referred to the physician managing their asthma if unexpected worsening of asthma is observed or reported. Subjects without a medical history of asthma who experience respiratory changes (exam findings or newly-reported signs and/or symptoms suggestive of asthma) should be referred to a respiratory specialist.

## 8.6.9.3 Spirometry/Peak Expiratory Flow

All subjects will have spirometry (PEF) performed at screening and baseline. For subjects reporting a medical history of asthma, spirometry (PEF) will be performed at each visit during the clinical trial under the supervision of qualified study personnel. Subjects with a new (de novo) diagnosis of asthma will be evaluated by spirometry (PEF) at all visits after the diagnosis is first made.

Peak expiratory flow measurements should consist of 3 good efforts, with the best result documented. It is preferable that the PEF measurement be performed before noon or at the same time during each study visit whenever possible. Attempts should be made to withhold asthma medication on study visit days until after PEF testing is complete, to the extent it does not pose an undue risk to the subject, to avoid interference with PEF measurements. Subjects with a PEF < 80% of the predicted value should be referred to a respiratory specialist.

## 8.6.9.4 Respiratory Referrals

Subjects with a medical history of asthma must be referred to the physician who manages their asthma when:

- PEF < 80% of the predicted value.
- ACT score ≤ 19. As an ACT score ≤ 19 conveys asthma that may not be adequately
  controlled.
- Unexpected worsening of asthma is observed or reported.

Subjects without a medical history of asthma must be referred to an appropriate specialist physician when:

- Signs and/or symptoms suggestive of asthma are newly-observed or reported.
- Respiratory assessment suggests a decline in the subject's respiratory health.

### 8.6.10 Electrocardiogram

A 12-lead Electrocardiogram (ECG) will be performed according to Section 7.2. ECGs for each subject should be obtained using the same electrocardiograph machine whenever possible. To minimize variability, subjects must remain in a resting position for at least 10 minutes before each ECG recording. Environmental distraction should be avoided during the pre-ECG resting period and during ECG recording. ECGs should be performed before any scheduled vital sign measurements and blood draws. For safety monitoring, the investigator or qualified designee must review, sign and date all ECG tracings. Paper ECG recordings will be kept as part of the subject file at the study center. All abnormal ECG findings considered to be clinically significant by the

CONFIDENTIAL Page 71 of 99

investigator at the screening visit will be recorded. Any clinically significant changes from the screening visit will be reported as AEs in the CRF.

# 8.7 Independent Data Monitoring Committee

An IDMC consisting of independent experts will review and monitor the accumulating safety data for the study on an ongoing basis.

The specific responsibilities and composition of the IDMC are outlined in a separate document, the IDMC Charter. The details of outputs provided for the meetings are also referenced in this separate IDMC Charter.

CONFIDENTIAL Page 72 of 99

#### 9 Statistical Methods

A Statistical Analysis Plan (SAP) will be developed as a separate document. The SAP will contain detailed and technical descriptions of specific data conventions, calculations and of statistical procedures for executing the analyses that are specified in the sections of the protocol below. Any changes made to the analysis after finalization of the SAP will be documented in the clinical study report.

The final statistical analysis will include all subjects who have completed the study. An interim analysis focused on PK and safety will be performed after approximately 10 subjects have completed the Week 8 visit as the basis to allow recruitment of adolescent subjects in the planned Phase 3 pivotal studies.

#### 9.1 Data Transformations

Details of any data transformation for endpoints will be provided in the SAP.

# 9.2 Analysis Populations

The following populations and evaluability criteria will be used to analyze the pharmacokineticpharmacodynamic (PK/PD), safety, efficacy, and QoL endpoints.

# 9.2.1 PK Analysis Population

The PK analysis population will include all subjects in the safety population who provide at least one post-baseline evaluable drug concentration value. All PK and PK/PD endpoints will be analysed using the PK population.

# 9.2.1.1 Safety Population

The safety population will comprise all subjects in the ITT population who receive at least one dose of study drug. Subjects will only be excluded if there is clear documented evidence that the subject did not receive any study drug injection. All safety data will be summarized based on the safety population.

# 9.2.2 Intent-to-Treat (ITT) Population

The ITT population will consist of all enrolled subjects. All efficacy endpoints will be analyzed based on the ITT population.

CONFIDENTIAL Page 73 of 99

# 9.3 Imputation of Missing Data

The primary method to impute the missing values for the efficacy assessments will be as follows:

Continuous Endpoints: To impute the missing values for efficacy continuous endpoints, Last Observation Carried Forward (LOCF) approach will be used. In addition, Observed Case (OC) will be carried out as sensitivity analysis.

**Binary Endpoints:** All missing values will be treated as a Non-Responder for the binary endpoints. LOCF and OC will be used as sensitivity analysis to impute the missing values.

Use of Rescue Therapy: All Efficacy Data, Except OC, Will Be Set To Missing After Rescue Medication Is Used. In OC Analysis, No Observed Data After Subject Has Received Rescue Treatment Will Be Excluded.

There will be no imputations for PK, missing laboratory, and vital sign data. Further details on imputation of missing data will be provided in the SAP.

# 9.4 Descriptive and Inferential Statistical Analyses

# 9.4.1 Demography and Baseline Characteristics

Subject disposition, demographics, baseline characteristics, previous therapies, concomitant therapies, and physical examinations will be summarized by descriptive statistics. Pre- and post-treatment therapies and procedures will be summarized separately.

# 9.4.2 PK Parameters and ADA Analyses

The PK parameters obtained using modelling techniques will be regarded as primary endpoints for the PK analyses (see details in Section 6.4.1). Primary inference for all the PK parameters will be based on the pharmacokinetic analysis population.

The PKPD relationship between nemolizumab plasma concentrations and the selected clinical outcomes (EASI, IGA and NRS) will be investigated, as appropriate, using a PKPD model development based on previous clinical data.

The pop-PK and PKPD models will be detailed in a separate Modeling Analysis Plan.

The concentration at each time point will be summarized as arithmetic mean, standard deviation, median, minimum, and maximum, number of BLQs (Below the Limit of Quantification).

Descriptive statistics (n, arithmetic mean, standard deviation [SD], minimum, median, maximum) will be calculated for all PK parameters obtained using NCA.

For ADA analyses, the incidence of positive ADA results will be summarized (absolute occurrence, percent of subjects, treatment-related ADA). A presentation of ADA results will be detailed in the SAP.

CONFIDENTIAL Page 74 of 99

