#### 8.3 Immunogenicity

Blood samples will be collected according to Section 7.2 to assess anti-drug (anti-nemolizumab) antibodies (ADA). Serum samples will be assessed for ADA at baseline, Weeks 4, 8, 16, 24 and at any unscheduled visit for safety reasons. ADA will be determined at these time points by the designated CRO using a validated enzyme-linked immunosorbent assay (ELISA) screening assay. The serum concentration will be assessed using a multi-tiered approach.

If serum circulating ADA is detected, presence will be confirmed and characterized (eg, for neutralizing potential) using a validated assay. Incidence of positive ADA results will be summarized (absolute occurrence and percent of subjects).

		Results
will be CSR.		included as an appendix in the final
8.4	Pharmacodynamics	
	and stratum corneum samples will be collected to inve d biomarkers.	estigate the effect of nemolizumab on
Blood s	samples will be collected for assessment of TARC a	and IgE by the central laboratory.

CONFIDENTIAL Page 59 of 99

Protocol Number: RD.06.SPR.116912	Version 6.0

21-JUL-2020

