6.1. General Methods

This section describes analytical analysis issues that relate to all or some of the analytic analysis sections that follow. It describes general guidelines for analysis as well as the following items:

- SAS version 9.4 or higher will be used.
- CCI will be responsible for reporting the demographic, safety, and efficacy data including listings of the administration information for collection of PK and PD samples.
- Unless otherwise specified, summaries will be presented by visit.
- The total number of subjects in the treatment group (N) will be used as the denominator for percentage calculations, unless stated otherwise in the table shell.
- Continuous variables will be summarized using the number of observations (n), mean, standard deviation (SD), median, minimum, and maximum. Categorical variables will be summarized using number of observations (n) and percentages of subjects.
- Subject data listings will be presented with the ITT population for efficacy assessments, with the Safety Population for safety assessments and with the PK population for PK assessments, unless stated otherwise.
- In general, the listings will be sorted by subject number, and assessment date (and time) if applicable.
- Multiple assessments at a given time point (repeat, and unscheduled) will not be included in summary tables unless specified otherwise, but will be included in the listings.

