9.1. Pharmacokinetic Concentration Presentation

Serum concentration data (unit: ng/mL) will be summarized by visit from baseline to Week 24 using the following statistics: n, arithmetic mean, standard deviation, %CV, geometric mean, %CV geometric mean, median, minimum, maximum, 95% CI of mean and number of BLQs (Below Limit of Quantification). BLQ will be considered as missing and excluded from the descriptive summary.

Individual serum concentration and mean concentration will be plotted by visit on both a linear and semi-logarithmic scale on the PK population (unit for x axis: week). For individual concentration plot, BLQ will be considered as missing. For mean concentration plot, mean concentration not calculated will be considered as missing. In addition, individual serum concentration will be plotted over time with different color for subjects with treatment related ADA+ (ADA- at baseline & ADA + after treatment), ADA + at baseline and ADA- from baseline during the study.

Individual serum concentrations will be listed and BLQ will be listed as BLQ.

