10.9. Other Safety

Confirmed pregnancy test results, childbearing potential, premense status results, biomarker and virology assessment data will be presented in a listing.

11. Immunogenicity

Blood samples will be collected to assess anti-drug (anti-nemolizumab) antibodies (ADA). Serum samples will be assessed for ADA at Baseline, Weeks 4, 8, 16, 24 and at any unscheduled visit for safety reasons.

Screening ADA, confirmation ADA, ADA titer, nutralizing antibodies, and treatment-related ADA will be will be summarized for the Safety population (scheduled visits only).

A treatment-related ADA is a post-baseline confirmatory ADA sample showing positive results while the baseline sreening or confirmatory ADA sample shows negative results.

All Immunogenicity data will be listed for the Safety population.

12. Health Economics

Not applicable.

13. Interim Analyses

An interim analysis is planned after approximately 10 subjects complete the Week 8 visit. The study will attempt to enrol at least 3 subjects with a low body weight (≤ 61 kg) for the interim analysis and approximately 6 total subjects with low body weight for the overall study population, with investigators attempting to enrol subjects at the lower age range (12-14 years old). The interim analysis will assess whether the observed safety and PK data from adolescents are similar to the data obtained in adults, which is the basis for allowing recruitment of adolescent subjects into the planned nemolizumab Phase 3 studies for AD (pivotal and open-label extension protocols).

Outputs presented for the interim analysis and for the IDMC are marked in Sections 18 (Index of Tables), Section 19 (Index of figures) and Section 20 (Index of Listings). But the selected output list for IDMC meeting can be updated by IDMC member's request.

14. Changes from Analysis Planned in Protocol

No changes to the methods planned in the protocol are foreseen.

15. Reference List

Not applicable.

16. Programming Considerations

All TLFs and statistical analyses will be generated using SAS® 9.4 or higher (SAS® Institute Inc., Cary, NC, USA). Computer-generated table, listings and figures (TLF) output will adhere to the following specifications.

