16.2.5.2. Table Conventions

- Units will be included where available
- If the categories of a parameter are ordered, then all categories between the maximum and
 minimum category are presented in the table, even if n=0 for dose group in a given category that is
 between the minimum and maximum level for that parameter. For example, the frequency
 distribution for symptom severity would appear as:

Severity	N
Rating	
severe	0
moderate	8
mild	3

Where percentages are presented in these tables, zero percentages will not be presented and so counts of 0 will be presented as 0 and not as 0 (0.0).

- If the categories are not ordered (e.g., Medical History, Reasons for Discontinuation from the Study, etc.), then only those categories for which there is at least 1 subject represented are included.
- An Unknown or Missing category are added to each parameter for which information is not available for 1 or more subjects.
- Unless otherwise specified, the estimated mean and median for a set of values are printed out to 1 more significant digit than the original values, and standard deviations are printed out to 2 more significant digits than the original values. The minimum and maximum should report the same significant digits as the original values. For example, for systolic blood pressure:

n	XX
Mean	XXX.X
SD	X.XX
Median	XXX.X
Min	XXX
Max	XXX

- Percentage values are printed to one decimal place, in parentheses with no spaces, one space after the count (e.g., 7 (12.8), 13 (5.4)). Pre-determine how to display values that round down to 0.0. A common convention is to display as '<0.1', or as appropriate with additional decimal places. Unless otherwise noted, for all percentages, the number of subjects in the analysis population for the treatment group who have an observation will be the denominator. Percentages after zero counts should not be displayed and percentages equating to 100% are presented as 100.0.

- Tabular display of data for medical history, prior/concomitant medications, and all tabular displays
 of adverse event data are presented by the body system, treatment class, or SOC. Within the

body system, drug class and SOC, medical history (by preferred term), drugs (by ATC code), and adverse events (by preferred term) are displayed in alphabetically order. If incidence for more than 1 term is identical, they should then be sorted alphabetically. Missing or not calculated descriptive statistics or p-values which cannot be estimated are reported as "-".

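### The protocol promises ADA incidence as a percent of subjects, but the SAP specifies no subject-level count across post-baseline samples and leaves off-schedule samples out of the summary

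*Protocol*

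**What the plan says.** **Protocol.** Section 6.2.2 lists ADA assessments, including neutralizing antibody (NAb), as a primary endpoint at baseline, Weeks 4, 8, 16 and 24, and at unscheduled visits for safety reasons. Section 8.3 states: "Incidence of positive ADA results will be summarized (absolute occurrence and percent of subjects"). Section 9.4.2 repeats this ("the incidence of positive ADA results will be summarized (absolute occurrence, percent of subjects, treatment-related ADA") and defers the presentation to the SAP. Section 7.6.2 makes an ADA sample compulsory at an unscheduled safety visit, and the schedule in Section 7.2 includes one at early termination.

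**SAP.** Section 11 says that screening and confirmatory ADA, titer, NAb and "treatment-related ADA will be will be summarized for the Safety population (scheduled visits only"). It then defines the term: "A treatment-related ADA is a post-baseline confirmatory ADA sample showing positive results", given a negative baseline. It names no statistic, denominator or any-post-baseline count. Two general rules in Section 6.1 fill the gap: "Unless otherwise specified, summaries will be presented by visit", and "The total number of subjects in the treatment group (N) will be used as the denominator for percentage calculations", the latter unless the table shell says otherwise. Section 16.2.5.2 has a different rule for percentages: unless otherwise noted, "the number of subjects in the analysis population for the treatment group who have an observation will be the denominator". Section 9.1 does classify people, as "subjects with treatment related ADA+ (ADA- at baseline & ADA + after treatment"), but only to colour the individual concentration plot. Section 14 declares no change from the protocol's methods.

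**The concern.** A percent of subjects who develop antibodies and a percent positive at a given visit are different quantities. The first counts each person once over the whole observation period. The second is a point prevalence, and it divides transient or staggered positivity among rows. If the SAP's defaults are followed, none of the rows in Table 14.3.4.5.1 is the proportion of adolescents who formed antibodies.

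Two further gaps add to this. A subject whose only positive sample came from an unscheduled safety visit would appear in the listing but in no summary row, although the endpoint includes those visits. And two programmers following different sections of the SAP could print different percentages from the same data.

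**Working it through.** The documents give no expected ADA rate, rollover rate or missing-sample rate, and N = 20 has no formula behind it, so there is no planned figure to reproduce. The counts below are assumptions chosen to show the range.

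**Inputs.** N = 20 (protocol 9.5, SAP 3.5). Four scheduled post-baseline ADA visits: Weeks 4, 8, 16 and 24 (SAP 11). Week 24 is attended only by subjects who do not roll over into the extension study (protocol 7.6).

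**1. By-visit prevalence against ever-positive incidence, same N.** Let p_v be the number of treatment-related positive subjects at visit v, and E the number positive at one or more of the four visits. Then max(p_v) ≤ E ≤ p_4 + p_8 + p_16 + p_24 ≤ 4 × max(p_v). Incidence therefore lies between one and four times the largest row.

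| Assumed pattern, E = 4 | Each by-visit row | Incidence |
|---|---|---|
| All four persistent from Week 4 | 4/20 = 20% | 4/20 = 20% |
| Each positive once, at a different visit | 1/20 = 5% | 4/20 = 20% |

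The exact (Clopper-Pearson) 95% CI for 4/20 is 5.7% to 43.7%. If positive samples were instead pooled over visits, the error would reverse: four persistent subjects give 4 × 4 = 16 positive results.

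**2. Off-schedule samples.** SAP 11 limits the summary to scheduled visits, and SAP 6.1 keeps unscheduled assessments out of tables by default. SAP 6.6 assigns unscheduled and early termination visits to analysis windows for efficacy, but not for safety or PK data. A subject positive only at an unscheduled safety visit thus adds 0/20 to every row and 1/20 = 5% to the true incidence. The same appears to hold for early termination samples. Section 6.6 does not name ADA data, so that part is an inference.

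**3. Denominator.** Two positives, under each SAP rule:

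| Visit and assumption | Total N (6.1) | Subjects with an observation (16.2.5.2) |
|---|---|---|
| Week 16, 0 missing | 2/20 = 10% | 2/20 = 10% |
| Week 16, 4 missing | 2/20 = 10% | 2/16 = 12.5% |
| Week 24, 5 roll over | 2/20 = 10% | 2/15 = 13.3% |
| Week 24, 10 roll over | 2/20 = 10% | 2/10 = 20% |
| Week 24, 15 roll over | 2/20 = 10% | 2/5 = 40% |

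The conflict is minor at Week 16 and can be large at Week 24.

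**4. Comparison within the SAP.** Adverse events count each subject once per term (10.2). Urinalysis and IGA success name subjects with available data at the visit as the denominator (10.3, 8.2). Hematology and chemistry add last, minimum and maximum post-baseline values during treatment (10.3). Section 11 has no equivalent rule.

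**The case against.** The strongest reply is that the SAP has not chosen an understating analysis. Section 11 does not state a layout or denominator. Both come from general defaults, and the shell for Table 14.3.4.5.1, which is not in the documents, may override them. With one scheduled sample per subject per visit, a by-visit percent of positive samples is also a percent of subjects. The protocol never uses the term ever-positive, and the endpoint itself is listed by visit. With about 20 subjects and a full ADA listing, a reader could count the positives by hand.

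Much of this stands. A reader might infer that the SAP fixes the full safety N as the denominator, or that the reported rate will certainly be too low. The documents support neither. Section 16.2.5.2 points the other way on the denominator. Under that rule a Week 24 row could even exceed the incidence: if 16 of 20 roll over and one of the four sampled is positive, the row reads 1/4 = 25% against an incidence of 20% in the example above. With persistent ADA and complete sampling, the two measures coincide.

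The reply does not dispose of the omission. Incidence as a percent of subjects is what the protocol promises, and no SAP text specifies it. The restriction to scheduled visits is explicit in Section 11, not a default, and it excludes samples that the endpoint includes. A listing is not a pre-specified summary.

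**Conclusion.** The point holds as a gap in specification with a real consequence: followed as written, the rules can miss subjects who become ADA positive. Over a common N and scheduled samples only, the shortfall from the largest by-visit row to the incidence runs from none to a factor of four. Fourfold is the extreme, with every positive subject positive once and at a different visit. Off-schedule positives are lost in addition. The size in practice depends on how transient ADA is, how many subjects roll over and how many samples are missing, none of which the documents give.

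It would be tempting to add that ADA incidence is the figure compared with adults. The documents do not say so. The interim comparison with adults is of safety and PK data. The ADA table is flagged for the interim analysis, but no adult ADA rate or criterion appears. The case rests on immunogenicity being a primary endpoint whose promised summary is not specified.

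**What to change.** In SAP Section 11 and Table 14.3.4.5.1:

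- Add a row that counts each subject once as treatment-related ADA positive if negative at baseline and confirmed positive at any post-baseline sample, including unscheduled and early termination samples. The denominator is subjects with a baseline and at least one evaluable post-baseline ADA sample.
- Report subjects who are ADA positive at baseline separately.
- Add the corresponding subject-level row for NAb.
- Keep the by-visit rows, with the number of subjects sampled at that visit as the denominator.
- Reconcile the denominator rules in Sections 6.1 and 16.2.5.2.

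The cost is a short SAP amendment and one or two extra table rows from data already collected. The reported ADA rate may be higher than the by-visit rows alone would suggest.
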